8.4.2 Appropriateness of efficacy assessments

Tumor assessments performed every 6-12 weeks of study treatment are consistent with the standard clinical practice for patients with advanced NSCLC. Conducting tumor evaluations more than 6 weeks apart may expose a participant to an unnecessary treatment if the disease progression event takes place between the infrequent assessments or prevent early identification of progression and appropriate treatment.

8.5 Safety assessments

Safety assessments are specified below with Section 1.3 detailing when each assessment is to be performed.

For details on AE collection and reporting, refer to Section 8.7

As per Section 4.5, during a Public Health emergency as declared by Local or Regional authorities i.e., pandemic, epidemic or natural disaster, that limits or prevents on-site study visits, regular phone or virtual calls can occur (every 3 weeks or more frequently if needed) for safety monitoring and discussion of the participant's health status until it is safe for the participant to visit the site again.

Table 8-2 Physical Assessments

Assessment	Specification
Physical examination	A complete physical examination will include the examination of general appearance, skin, neck (including thyroid), eyes, ears, nose, throat, lungs, heart, abdomen, back, lymph nodes, extremities, vascular, and complete neurological examination. If indicated based on medical history and/or symptoms, rectal, external genitalia, breast, and pelvic exams will be performed. Complete physical examination will be performed at screening, C1D1 and at EOT A direct and oriented physical exam including the examination of general appearance, vital signs (blood pressure [SBP and DBP] and pulse) and complete neurological examination will be performed at all visits starting from C2D1 as per Table 1-3 except where a complete physical examination is required (see above). Information for all physical examinations must be included in the source documentation at the study site. Clinically relevant findings that are present prior to signing informed consent must be recorded on the appropriate eCRF that captures medical history. Significant findings made after signing informed consent which meet the definition of an Adverse Event must be recorded as an adverse event.
Vital signs	Vital signs include blood pressure (supine position preferred when ECG is collected), pulse measurement, respiratory rate and body temperature. They will be measured at screening and at subsequent timepoints as specified in Table 1-3.
Height and weight	Height in centimeters (cm) and body weight (to the nearest 0.1 kilogram (kg) in indoor clothing, but preferably without shoes) will be measured as specified in Table 1-3.
ECOG performance status	ECOG performance status will be measured at screening and at subsequent time points as specified in Table 1-3.

ECOG performance status scale will be used as described in Table 8-3 (Oken et al 1982).

Table 8-3 ECOG Performance Status

Grade	ECOG performance status
0	Fully active, able to carry on all pre-disease performance without restriction
1	Restricted in physically strenuous activity but ambulatory and able to carry out work of a light or sedentary nature e.g., light house work, office work
2	Ambulatory and capable of all self-care but unable to carry out any work activities. Up and about more than 50% of waking hours
3	Capable of only limited self-care, confined to bed or chair more than 50% of waking hours
4	Completely disabled. Cannot carry on any self-care. Totally confined to bed or chair
5	Dead

8.5.1 Physical examinations

Physical examination should be performed as specified in Table 8-2.

8.5.2 Vital signs

Vital signs should be monitored according to the instructions in Table 8-2.

8.5.3 Electrocardiograms

Electrocardiograms (ECGs) will be centrally evaluated and must be recorded after 10 minutes rest in the supine position to ensure a stable baseline. The preferred sequence of cardiovascular data collection during study visits is ECG collection first, followed by vital signs, blood sampling, and any remaining assessments for that visit.

The Fridericia QT correction formula (QTcF) must be used for clinical decisions, e.g., at Screening to assess eligibility. The Investigator must calculate corrected QT interval (QTc) if it is not auto-calculated by the ECG machine.

ECGs will be performed at screening, C1D1, C1D15 and at EOT (Table 8-4).

Triplicate 12 lead ECGs are to be recorded approximately 2 minutes apart. The mean QTc value for each visit will be calculated from the triplicate ECGs for each participant.

Table 8-4 Central ECG collection plan

Cycle	Day	Time	ECG Type
Screening		Anytime (before C1D1)	12 Lead, triplicate
1	1	Pre-dose and 4 hours post-dose (within 15 minutes prior to PK)	12 Lead, triplicate
1	15	Pre-dose and 4 hours post-dose (within 15 minutes prior to PK)	12 Lead, triplicate
EOT		Anytime	12 Lead, triplicate
Unscheduled	or Unplanned ECG	Anytime if clinically indicated	12 Lead, triplicate

In order to enable ECG evaluation by the central ECG laboratory for eligibility assessment, ECGs should be submitted to the central ECG laboratory prior to enrollment (to refer to the ECG manual for the turn around time).

In the event that a QTcF value of > 500 ms is observed or if an unscheduled ECG is performed for safety reasons, it is recommended to collect a time-matched PK sample and record the time

and date of the last study treatment intake to determine the drug exposure. Dose adjustments in case of QT prolongation should be performed per Section 6.5.

In the event that a clinically significant ECG abnormality is identified at the site (e.g., severe arrhythmia, conduction abnormality of QTcF > 500 ms), a copy of the assessment is sent to the central ECG laboratory for expedited review and the ECG is repeated at the site to confirm the diagnosis. If the participant is hemodynamically compromised, the Investigator or a medically qualified person must initiate appropriate safety procedures without delay (for example cardioversion).

All ECGs, including unscheduled safety ECGs with clinically relevant findings collected during the study need to be transmitted to the central ECG laboratory for review.

The original ECGs on non-heat sensitive paper or a certified copy on non-heat sensitive paper and appropriately signed must be archived at the study site.

Additional, unscheduled, safety ECGs may be repeated at the discretion of the Investigator at any time during the study as clinically indicated. For any ECGs with participant safety concerns, two additional ECGs must be performed to confirm the safety finding. ECG safety monitoring, or a review process, should be in place for clinically significant ECG findings at baseline before administration of study treatment and during the study.

Clinically significant abnormalities must be recorded on the eCRF as either medical history/current medical conditions or adverse events as appropriate.

8.5.3.1 Cardiac imaging - echocardiogram or cardiac magnetic resonance (CMR)

Echocardiogram or CMR to assess LVEF will be performed at screening, C2D1, at EOT and as clinically indicated.

This assessment will be performed locally. The modality of the cardiac function assessments must be consistent throughout the study i.e., if echocardiogram is used for the baseline assessment then echocardiogram should also be used for subsequent scans. The participant should also be examined using the same machine and operator whenever possible.

8.5.3.2 Cardiac enzymes

Creatine kinase (CK) assessment has to be performed at the same schedule as the other blood biochemistry tests. Isoenzyme (CK-MB) and Troponins (I and/or T) will be performed if clinically indicated by the Investigator (refer to Table 8-5).

8.5.4 Clinical safety laboratory tests

All laboratory parameters assessed for safety purposes (Table 8-5) will be evaluated centrally except for urinalysis (dipstick for macroscopic panel) and urine pregnancy tests (dipstick) that will be performed locally. In the case of any macroscopic out of range parameters, a urine sample will be sent to central laboratory for further analysis (microscopic panel). Dipstick for urinalysis test (macroscopic panel) and dipstick for urine pregnancy test will be performed unless local institution policies dictate otherwise. For China only, local laboratories can be used for all specimens collected (i.e, central laboratory assessments not mandatory).

Samples for these parameters will be collected prior to study treatment administration.

Local laboratory assessments may be performed if medically indicated or when the treating physician cannot wait for central laboratory results for decision making. In this particular situation, the blood sample obtained at the same time point should be submitted to the central laboratory for analysis in parallel with local analysis.

The results of the local laboratory will be recorded in the eCRF if the following criteria are met:

- A treatment decision was made based on the local results, or
- There are no concomitant central results available.

Laboratory values obtained during the Screening period from the central laboratory will be used to assess participant's eligibility.

The site does not need to wait for the results of centrally-analyzed laboratory assessments when an immediate clinical decision needs to be made (e.g., confirmation of eligibility, study treatment interruption, re-initiation, and/or termination) and in those cases locally unscheduled testing may be performed and used for eligibility assessments.

Details on the collections, shipment of samples and reporting of results by the central laboratory are provided to Investigators in the Laboratory Manual.

As per Section 4.5, during a Public Health emergency as declared by Local or Regional authorities i.e., pandemic, epidemic or natural disaster, that limits or prevents on-site study visits, if participants cannot visit the site for protocol specified safety lab assessments, an alternative lab (local) collection site may be used.

Table 8-5 Clinical laboratory parameters collection plan

Test Category	Test Name
Hematology	Hemoglobin, Platelets, Erythrocytes, Leukocytes, Erythrocyte Cell Morphology (if possible), Differential (Basophils, Eosinophils, Lymphocytes, Monocytes, Neutrophils in percentage or absolute)
Chemistry	Albumin, Alkaline phosphatase, ALT, AST, Gamma-glutamyl-transferase (GGT), Lactate dehydrogenase (LDH), Calcium, Magnesium, Phosphate, Sodium, Potassium, Creatinine, Creatinine clearance, Total Bilirubin, Direct Bilirubin (only if total bilirubin is ≥ grade 2), Blood Urea Nitrogen (BUN) or Urea, Serum Amylase, Lipase, Fasting Glucose (non-fasting allowed post-baseline), Bicarbonate, Chloride, Creatine Kinase (CK) Uric Acid at screening and thereafter if clinically indicated
Urinalysis	Macroscopic Panel (Dipstick) (Color, Bilirubin, Occult Blood, Macroscopic Blood, Glucose, Ketones, Leukocytes esterase, Nitrite, pH, Protein, Specific Gravity, Urobilinogen) Microscopic Panel if indicated, (Erythrocytes, Leukocytes, Casts, Crystals, Bacteria, Epithelial cells)
Coagulation	Prothrombin time (PT), International normalized ratio (INR), Activated partial thromboplastin time (APTT)
Liver event testing and liver follow-up testing	To refer to Section 10.5 (Liver safety monitoring)
Renal follow-up	To refer to Section 10.6 (Renal safety monitoring)
Pregnancy Test and assessment of fertility	Serum / Urine pregnancy test. If local requirements dictate otherwise, local regulations should be followed. Confirmatory serum pregnancy required in case of positive urine pregnancy test. Urine pregnancy test will be performed locally. Follicle Stimulating Hormone (FSH),

Test Category	Test Name
	Luteinizing Hormone (if required to confirm the menopausal status): these tests will be performed locally and documented in source document.
	At screening a serum pregnancy test is to be performed within 72 hr before the first dose, while during the study (Day 1 of each cycle) urine pregnancy tests are sufficient. An End of Treatment serum pregnancy test is also required to be performed.
	For women considered to be post-menopausal and not of childbearing potential, pregnancy testing is not required. If a serum pregnancy test is required as per local practice at day 1 of every cycle, the urine pregnancy test does not need to be repeated.
Cardiac enzymes	Isoenzyme (CK-MB) and Troponins (I and/or T) if clinically indicated.

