Signed informed consent must be obtained before any study specific assessments are performed, including those at molecular pre-screening and screening.

Main screening evaluations and baseline radiological tumor assessments should be performed within 28 days (and 42 days for whole body scan) of treatment start.

Laboratory assessments performed as part of the screening evaluations will not be required to be repeated on the first day of dosing (C1D1) (except for hematology/chemistry and serum pregnancy test if not done within 72 hours prior to treatment start) unless deemed clinically necessary by the Investigator and/or required as per local institutional policies.

Study treatment will begin on C1D1 with the first administration of the study treatment.

Treatment cycles are intended to last 3 weeks (21 days), but the treatment can be interrupted in order to manage toxicities according to the dose modification criteria in Section 6.5.

Please refer to Table 1-2 for allowable visits window.

 Table 1-2
 Allowable window for participant assessments

Visit name	Window
Screening	-28 days from the first dose of study treatment (-42 days for whole body scan)
C1D1	Within 3 days after IRT enrollment
C1D15 onwards	± 3 days
Imaging evaluations	± 7 days
ePRO (completion at home)	Within 3 days prior to the scheduled assessment
EOT	Within 7 days after stopping study treatment
30-day safety follow-up	+ 7 days
Survival	± 14 days

Table 1-3 Assessment Schedule

Period	Screening				Trea	atment		Follow-up				
Cycle					Су	/cle 1						
Visit Name	Molecular Pre- screening	Screening	Screening	Cycle 1		-	cle 2	Cycle 3 onwards	ЕОТ	Safety follow-up (30 days after last administration of study treatment)	Efficacy follow-up	Survival follow- up (every 12 weeks)
Days	0	-28 to -1	Day 1	Day 15	Day 1	Day 15	Day 1	ı	•	-	-	
Molecular Pre- screening Informed Consent	Х											
PD-L1 expression status per participant's record (local test result) or central test result	X											
Confirmation of KRAS G12C mutation status in tumor tissue or blood as per existing local result or central test when local is not available ¹	×											
Confirmation of STK11 mutation status in tumor tissue or blood as per existing local result or central test when local is not available (For cohort B only) ¹	х											

Period	iod Screening				Tre	atment		Follow-up					
Cycle					Cy	/cle 1		·					

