 - Aspartate transaminase (AST) ≤ 3 x upper limit of normal (ULN),
 - Alanine transaminase (ALT) ≤ 3 x ULN,
 - Total bilirubin ≤ 1.5 ULN,
 - Serum amylase $\leq 2 \times ULN$,
 - Serum lipase $\leq 1.5 \text{ x ULN}$,
 - Creatinine clearance ≥ 45 mL/min by calculation using Cockcroft-Gault formula.
- 10. Participant is capable of swallowing study medication and following instructions regarding study treatment administration, or have a daily caregiver(s) who will be responsible for administering study treatment.
- 11. Participant must be able to communicate with the Investigator and comply with the requirements of the study procedures.

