Febrile neutropenia (ANC < 1.0×10^9 /L, with a single temperature of >38.3 degrees C [101 degrees F] or a sustained temperature of \geq 38 degrees C [100.4 degrees F] for more than one hour)	Mandatory: Interrupt study treatment until resolved, then reduce 1 dose level.
Anaemia	
Grade 1 (Hemoglobin [Hgb] < LLN - 10.0 g/dL; < LLN - 6.2 mmol/L; < LLN - 100 g/L)	Recommendation: Maintain study treatment and dose level.
Grade 2 (Hgb < 10.0 - 8.0 g/dL; < 6.2 - 4.9 mmol/L; < 100 - 80 g/L)	Recommendation: Maintain study treatment and dose level.
Grade 3 (Hgb < 8.0 g/dL; < 4.9 mmol/L; < 80 g/L; transfusion indicated)	Recommendation: Interrupt study treatment until resolved to ≤ grade 2, then:
	If resolved in ≤ 7 days, resume study treatment at the same dose level;
	If resolved in > 7 days, reduce 1 dose level.
Grade 4 (Life-threatening consequences; urgent intervention indicated)	Mandatory: Interrupt study treatment until resolved to ≤ grade 2, then reduce 1 dose level.

Investigations (Renal)	
Serum creatinine	
Grade 1 (> ULN - 1.5 × ULN)	Recommendation: Maintain study treatment and dose level.
Grade 2 (> 1.5 - 3.0 × ULN)	Recommendation: Interrupt study treatment and manage according to institutional practice.
	Upon resolution to ≤ Grade 1, may reintroduce study treatment at the same dose level if clinically indicated.
Grade 3 (> 3.0 - 6.0 × ULN) and Grade 4 (> 6.0 × ULN)	Mandatory: Permanently discontinue study treatment.
Investigations (Hepatic)	
Isolated total Bilirubin elevation	
Grade 1 (> ULN – 1.5 × ULN)	Recommendation: Maintain study treatment and dose level.
Grade 2 (> 1.5 - 3.0 × ULN)	Recommendation: Interrupt study treatment.
	Repeat LFTs ^b within 48-72 hours, then monitor LFTs at least weekly, until resolved to ≤ 1.5 × ULN or to baseline, then:
	• If resolved in ≤ 7 days, resume study treatment at the same dose level;
	If resolved in > 7 days, reduce 1 dose level.
Grade 3 (> 3.0 - 10.0 × ULN)*	Recommendation: Interrupt study treatment.
	Repeat LFTs ^b within 48-72 hours, then monitor LFTs at least weekly, until resolved to ≤ 1.5 × ULN or to baseline. May reintroduce study treatment at 1 lower dose level if clinically indicated.
Grade 4 (> 10.0 × ULN)*	Mandatory: Permanently discontinue study treatment.
	The participant should be monitored at least weekly (including LFTs ^b), or as clinically indicated, until total bilirubin has resolved to ≤ 1.5 × ULN or to baseline.

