	Repeat LFTs ^b as soon as possible, preferably within 48-72 hours from awareness of the abnormal results; monitor LFTs ^b at least weekly, until resolved to baseline or stabilization over 4 weeks.	
Combined ^c elevations of AST or ALT and total biliru	ıbin	
For participants with normal baseline ALT and AST and total bilirubin value:	Mandatory: Interrupt study treatment and adjudicate for DILI:	
AST or ALT >3.0 × ULN combined with total bilirubin > 2.0 × ULN without evidence of cholestasis ^d and Gilbert's syndrome For participants with elevated baseline AST or	Repeat as soon as possible, preferably within 48 hours from awareness of the abnormal results, monitor LFTs ^b at least weekly, or as clinically indicated, until AST, ALT, and total bilirubin have resolved ≤ Grade 1 or to baseline.	
ALT or total bilirubin value: AST or ALT > 3 × baseline OR > 8.0 × ULN.	If causality assessment indicates that DILI is	
whichever is lower, combined with total bilirubin > 2 ×	confirmed: Permanently discontinue study treatment.	
baseline AND > 2.0 × ULN Note: For participants with Gilbert's syndrome, at least 2-fold increase in direct bilirubin.	If not DILI: Treat the identified cause according to institutional guidelines. Once resolved to ≤ Grade 1 or to baseline, may reintroduce study treatment at 1 lower dose level if clinically indicated, following discussion with Novartis medical monitor.	
	Refer to Section 6.5.3.1 for further details on the follow up of potential drug-induced liver injury (DILI) cases.	
Investigation (metabolic)		
amylase and/or lipase elevation		
Grade 1 (> ULN - 1.5 × ULN)	Recommendation: Maintain study treatment and dose level.	
Grade 2 (> 1.5 - 2.0 × ULN)	Recommendation: Maintain study treatment and dose level.	

Grade 3 (> 2.0 - 5.0 × ULN) with signs or symptoms; > 5.0 × ULN and asymptomatic.**	Recommendation: Interrupt study treatment until resolved to Grade ≤ 1 or baseline, then:	
	If resolved in ≤ 7 days, resume study treatment at the same dose level.	
	If resolved in > 7 days, reduce 1 dose level.	
Grade 4 (> 5.0 × ULN with signs or symptoms)**	Mandatory: Permanently discontinue study treatment.	
Cardiac Investigations		
Left Ventricular Ejection Fraction (LVEF)		
LVEF < 40%	Mandatory: Interrupt study treatment, obtain consultation with cardiologist and repeat cardiac imaging after 3 weeks. If improved to > 45%, restart study treatment at the same dose. If not improved to >45%, permanently discontinue study treatment.	

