Transaminase increase combined with total bilirubin increase may be indicative of potentially severe DILI. These cases should be considered as clinically important events and assessed appropriately to establish the correct diagnosis. The required clinical information, as detailed below, should be sought to obtain the medical diagnosis of the most likely cause of the observed laboratory abnormalities.

The threshold for potential DILI may depend on the participant's baseline AST/ALT and total bilirubin value; participants meeting any of the following criteria will require further follow-up as outlined below:

- For participants with normal ALT and AST and total bilirubin value at baseline: AST or ALT $> 3.0 \times ULN$ combined with total bilirubin $> 2.0 \times ULN$
- For participants with elevated AST or ALT or total bilirubin value at baseline: [AST or ALT >3.0 × baseline] OR [ALT or AST > $8.0 \times ULN$], whichever occurs first, combined with [total bilirubin $> 2.0 \times$ baseline AND $> 2.0 \times$ ULN]

As DILI is essentially a diagnosis of exclusion, other causes of abnormal liver tests should be considered and their role clarified before DILI is assumed to be the cause of liver injury.

A detailed history, including relevant information such as review of ethanol consumption, concomitant medications, herbal remedies, supplement consumption, history of any preexisting liver conditions or risk factors, should be collected.

Laboratory tests should include ALT, AST, total bilirubin, direct and indirect bilirubin, Gamma-glutamyl transferase (GGT), prothrombin time (PT)/ International Normalized Ratio (INR), alkaline phosphatase, albumin, and creatine kinase. If available, testing of Glutamate Dehydrogenase (GLDH) is additionally recommended.

Evaluate status of liver metastasis (new or exacerbation) or vascular occlusion – e.g. using CT, Magnetic Resonance Imaging (MRI), or duplex sonography.

Perform relevant examinations (Ultrasound or MRI, Endoscopic retrograde cholangiopancreatography (ERCP)) as appropriate, to rule out an extrahepatic cause of cholestasis. Cholestasis (is defined as an ALP elevation > 2.0 × ULN with R value < 2 in participants without bone metastasis, or elevation of the liver-specific ALP isoenzyme in participants with bone metastasis).

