Any clinical event of jaundice (or equivalent term)
• ALT or AST > 3 x ULN accompanied by (general) malaise, fatigue, abdominal pain, nausea, or vomiting, or rash with eosinophilia
Any adverse event potentially indicative of a liver toxicity
ALT or AST > 3 x baseline or > 300 U/L (whichever occurs first)

Table 10-2 Follow-up requirements for liver laboratory triggers - ALT, AST, bilirubin

ALT	TBL	Liver Symptoms	Action
ALT increase without bilirubin increase:			

เพองสเนธ	Cornidential
Amended Protocol Version No.01 (Clean)	
•	

ALT	TBL	Liver Symptoms	Action
If normal at baseline: ALT > 3 x ULN If elevated at baseline: ALT > 2 x baseline or > 300 U/L (whichever occurs first)	Normal For participants with Gilbert's syndrome: No change in baseline TBL	None	· No change to study treatment · Measure ALT, AST, ALP, GGT, TBIL, INR, albumin, CK, and GLDH in 48-72 hours. · Follow-up for symptoms.
If normal at baseline: ALT > 5 x ULN for more than two weeks If elevated at baseline: ALT > 3 x baseline or > 300 U/L (whichever occurs first) for more than two weeks	Normal For participants with Gilbert's syndrome: No change in baseline TBL	None	· Interrupt study treatment · Measure ALT, AST, ALP, GGT, TBIL, INR, albumin, CK, and GLDH in 48-72 hours. · Follow-up for symptoms.
If normal at baseline: ALT > 8 x ULN	Normal	None	Initiate close monitoring and workup for competing etiologies.
ALT increase with bilirub	in increase:		· Study treatment can be
If normal at baseline: ALT > 3 x ULN	TBL > 2 x ULN (or INR > 1.5)	None	restarted only if another etiology is identified and liver enzymes return to
If elevated at baseline: ALT > 2 x baseline or > 300 U/L (whichever occurs first)	For participants with Gilbert's syndrome: Doubling of direct bilirubin		baseline.
If normal at baseline: ALT > 3 x ULN	Normal or elevated	Severe fatigue, nausea, vomiting, right upper	
If elevated at baseline: ALT > 2 x baseline or > 300 U/L (whichever occurs first)		quadrant pain	

Follow-up requirements for liver laboratory triggers - isolated hyperbilirubinemia **Table 10-3**

Criteria	Actions required	Follow-up monitoring
Total Bilirubin (isolated)	7 totalono roquirou	Tonon up monitoring
>1.5 – 3.0 ULN	Maintain treatment Repeat LFTs within 48-72 hours	Monitor LFTs weekly until resolution to ≤ Grade 1 or to baseline

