2.1.3.7 Baseline

For safety and efficacy evaluations, the last available assessment on or before the date of start of study treatment is defined as “baseline” assessment.

If labs with duplicate laboratory measurements taken at the last assessment date on or before the start date of study treatment, then the rule described below will be applied for the calculation of baseline.

If values are from central and local laboratories, the value from central assessment should be considered as baseline.

For gradable labs:

- The value of lower CTCAE grade will be considered as the baseline value.
- If several records have the same absolute grade, but in different directions, two baselines should be created, the record with grade below 0 should be the baseline of the 'Hypo' parameter, and the other record should be the baseline for the 'Hyper' parameters.

For non-gradable labs:

- If both within normal range: take average value
- If one within normal range and the other outside: take the one within normal range
- If both outside normal range: take the one closest to the normal range

If participants have no value as defined above, the baseline result will be missing.

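### No direct bilirubin is planned before dosing for a participant within the entry limit, so the 2-fold direct-bilirubin rule for Gilbert's syndrome has no planned reference value

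*Protocol*

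**What the plan says.** **Collection.** Protocol Section 8.5.4, Table 8-5, lists in the chemistry panel "Total Bilirubin, Direct Bilirubin (only if total bilirubin is ≥ grade 2". Chemistry is drawn at screening. Under Section 1.3, screening laboratory tests need not be repeated on C1D1, "except for hematology/chemistry and serum pregnancy test if not done within 72 hours prior to treatment start". The same Table 8-5 panel applies on both occasions.

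**Entry.** Section 5.1, criterion 9, requires "Total bilirubin ≤ 1.5 ULN". There is no separate limit for Gilbert's syndrome.

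**Grade boundary.** In Table 6-3, the row for isolated total bilirubin elevation gives "Grade 2 (> 1.5 - 3.0 × ULN" as the range.

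**Use.** In Table 6-3, the row for combined AST/ALT and bilirubin elevation carries a note for participants with Gilbert's syndrome: "at least 2-fold increase in direct bilirubin". The action on that row is mandatory: interrupt treatment, adjudicate for drug-induced liver injury (DILI), and discontinue permanently if it is confirmed. Table 10-2 (Section 10.5) has the parallel entry "Doubling of direct bilirubin" for ALT increase with bilirubin increase.

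**Missing baseline.** SAP Section 2.1.3.7 takes the last value on or before the start of treatment and adds: "If participants have no value as defined above, the baseline result will be missing".

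**The concern.** The protocol foresees participants with Gilbert's syndrome and gives them their own bilirubin criterion. That criterion is a ratio of two direct bilirubin values, and the collection plan does not schedule the earlier one. If such a participant has a qualifying ALT or AST rise on treatment, the site may be unable to say whether a mandatory interruption rule has been met. Section 6.5.1 does not allow deviations from mandatory interruptions. A pre-dose value cannot be recovered once dosing has begun, unless the sample was kept.

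In Table 10-2 the same entry separates two courses of action. With ALT above 3 × ULN, total bilirubin unchanged from baseline and no symptoms, treatment continues. Once direct bilirubin has doubled, treatment may restart only if another cause is found and liver enzymes return to baseline.

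**Working it through.** The plan states no figure to reproduce. The check compares thresholds and then searches for another source of the value.

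**Step 1: can a sample within the entry limit trigger the direct test?** Let T be total bilirubin before dosing, in multiples of ULN.

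| Condition | Source | Range |
|---|---|---|
| Entry | Section 5.1, criterion 9 | T ≤ 1.5 |
| Direct bilirubin is run | Table 8-5 (Grade 2 or higher), with the Table 6-3 total-bilirubin row | T > 1.5 |

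The two ranges do not overlap. A pre-dose sample within the entry limit is therefore not fractionated under the protocol.

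**Step 2: does anything else supply a planned pre-dose direct value?** Every other mention of direct, conjugated or indirect bilirubin concerns an on-study event:

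- Table 6-3, footnote b: core liver tests are fractionated only if total bilirubin exceeds 2.0 × ULN, a higher trigger.
- Table 6-3, asterisked note: total bilirubin above 3.0 × ULN due to the indirect component only.
- Section 6.5.3.1: "Laboratory tests should include ALT, AST, total bilirubin, direct and indirect bilirubin". This belongs to the work-up after the DILI thresholds have been met.
- Table 10-1: the conjugated fraction in the definition of a potential Hy's Law case.
- Table 10-3: the haemolysis test when isolated total bilirubin is above 3 × ULN.

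A pre-dose value can still arise by chance. Total bilirubin may exceed 1.5 × ULN on C1D1, a first screening value may have been above the limit before a retest, or the site may have ordered the test locally. None of these is planned.

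**Step 3: what can be concluded without the reference?** Let T0 be baseline total bilirubin (measured), d0 baseline direct bilirubin (not measured) and D direct bilirubin at the event, all in the same unit. Direct cannot exceed total, so 0 ≤ d0 ≤ T0.

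- The criterion is D ≥ 2 × d0.
- It is certain to be met only if D ≥ 2 × T0, the worst case d0 = T0. For a participant at the entry limit this means D ≥ 2 × 1.5 = 3.0 times the ULN for total bilirubin.
- For any smaller D above zero the answer is open: d0 could be at or below D/2 (criterion met) or above it (not met).

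**Step 4: is the event value itself available?** That depends on how the Gilbert's note in Table 6-3 is read.

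- If it adds to the total-bilirubin condition, a qualifying sample has total bilirubin above 2.0 × ULN. That is already Grade 2 or higher, so direct bilirubin is run on it and only d0 is missing.
- If it replaces that condition, an event sample with total bilirubin at or below 1.5 × ULN is not fractionated either, and both D and d0 can be missing.

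The wording does not settle this. The normal-baseline part of the row appears to exclude Gilbert's syndrome, which favours replacement.

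**Step 5: the SAP.** The liver summaries and the potential Hy's Law definition in SAP Section 2.9.3 use total bilirubin. No planned analysis depends on the missing value.

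**The case against.** The threshold comparison is hard to dispute. The case against concerns its consequences.

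- **The reference need not be pre-dose.** Neither Gilbert's entry names baseline as the comparator for direct bilirubin. Chemistry is repeated through treatment, and any earlier on-study sample above 1.5 × ULN would have been fractionated. This stands in part: some participants will have an earlier value. It arises only by chance, though, and is measured on drug, when the liver may already be affected.
- **Other rules cover the participant.** Where the combined thresholds are not met, a Table 6-3 footnote sends the site to the isolated rows and asks for conservative action. Those rows recommend interruption for total bilirubin above 1.5 × ULN and, with normal baseline transaminases, for ALT or AST above 3.0 × ULN. Section 6.5.3.1 sets its DILI thresholds on total bilirubin, and Table 10-2 also has INR and symptom entries. This stands and limits the harm. However, the isolated rows at these levels are recommendations, and Section 6.5.3.1 sets out follow-up without itself ordering interruption. The mandatory interruption and adjudication step stays undetermined.
- **The Laboratory Manual may already ask for it.** Section 8.5.4 refers to that manual for collection and reporting details, and it was not available. The possibility remains open, but Table 8-5 is the protocol's collection plan and makes the test explicitly conditional.

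**Conclusion.** The concern holds and is minor. Followed exactly, Table 8-5 leaves a stated mandatory safety criterion without its planned reference value for any participant with Gilbert's syndrome who is within the entry limit before dosing.

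Few participants are likely to be affected. The documents give neither the frequency of Gilbert's syndrome nor the rate of qualifying liver events, so no number can be derived. The effect is confined to one note in Table 6-3 and one entry in Table 10-2. No endpoint changes.

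The conclusion assumes that the 2-fold increase and the doubling are measured against a value from before treatment. The documents imply this without saying so. It also assumes that the Laboratory Manual does not add the test. The finding is firm for the protocol text and less so for what laboratories will report in practice.

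**What to change.** 1. In Table 8-5, report direct bilirubin on the existing screening or C1D1 pre-dose chemistry sample for all participants, or at least for those with known Gilbert's syndrome.
2. Report it also on any on-study sample from a participant with Gilbert's syndrome that meets the ALT/AST part of the criterion.
3. State in Table 6-3 whether the Gilbert's note replaces the total-bilirubin condition or adds to it. If it adds, direct bilirubin is already run on every qualifying sample and item 2 is not needed.

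The cost is one extra analyte on blood already drawn, plus the wording changes. No new visit or sample is needed, and the SAP analyses stay as they are.
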